### 5.5 Withdrawal of Participation

Participants are free to withdraw from the study and to opt-out at any point or a participant can be withdrawn by the Investigator. If withdrawal occurs, the participant will have the option as to whether they wish to allow previously collected data to be utilised for ongoing research. The reason for withdrawal will be documented in the participant's case report form (CRF) although a reason would not have to be provided.

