#### 6.2 Baseline Assessments

#### For Substudy 1

The following assessments will occur following informed consent during the initial consultation. These are validated questionnaires and post hoc analysis will allow us to probe whether any of these questionnaires can help stratify in which patients home EEG will be feasible for future trials.

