#### 9.5 Data Loss

The technology used in the study will be set up for each participant according to a rigorous protocol agreed by the research team, and participants are provided with written and verbal information on study activities to ensure adherence to protocol. However due to the remote and technology-focused nature of the study, it is possible for data to be lost or not collected due to technological issues (e.g., battery failures).

If a significant portion of data is missing on a given task, participants may be asked if they are willing to repeat an EEG night or blood test if appropriate within the 3 month study period. The participant can decline repeating any measures without this affecting their participation in the study. Similarly, if appropriate in the opinion of the Chief Investigator, participants may be asked to complete study activities outside of their main study period if study protocol has changed (and participants will be reconsented as appropriate).

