### 10.2 Proposed Analyses

#### For Substudy 1

Data analysis will:

- a) Quantify the proportion of missing data for sleep nights with high density EEG. Post hoc analysis will also explore whether any baseline questionnaire outcomes associate with poor data quality (larger levels of missing data)
- b) Calculate acceptability ratings for home EEG
- c) We will analyse non-REM duration from high density EEG and assess whether or not we can replicate the observed association between sleep metrics and memory observed from laboratory polysomnography, e.g. in the DOPAMIND study, when using home high density EEG.
- d) Quantify the proportion of datasets for sleep nights with pulse oximetry which are sufficiently complete to enable clinical screening for Obstructive Sleep Apnoea.

### For Substudy 2

Analysis of samples: will be on using the SIMOA platform for research use.

SleepAD Protocol v6.0 6th September 2024

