### 14.2 Quality Assurance

#### 14.2.1 Accuracy of Case Report Forms

Paper case report forms (CRFs) and electronic patient-reported outcomes (PROs) are the primary data collection instruments for the study. The Principal Investigator, or a designee will record data collected on each subject. The Principal Investigator will be responsible for the timing, completeness, legibility and accuracy of the CRF and will retain a copy of each completed form.

For paper CRFs: All data requested on the CRF will be recorded and checked by a member of the study team. All missing data will be explained. If a space on the CRF is left blank because the procedure was not done or the question was not asked, "N/D" will be inserted. If the item is not applicable to the individual case, "N/A" will be inserted. All entries will be printed legibly in ink. If any entry errors are made, to correct such an error, a single straight line will be drawn through the incorrect entry and the correct data entered above it. All such changes will be initialled and dated. Pencil and correction fluid will not be used anywhere on the CRF. If it is not clear why the change has been made, an explanation will be written next to the change. Paper CRFs will be entered into a University of Bristol approved electronic data capture system.

Each participant enrolled into the study must have the correct CRFs completed and signed by the Principal Investigator (or designee). This also applies to those participants who failed to complete the study. All data submitted on CRFs must be verifiable in the source documentation or the discrepancies explained.

SleepAD Protocol v6.0 6th September 2024

If a participant withdraws from the study during the experiment phase, the reason must be noted on the Withdrawal Form.

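### The home-EEG missing-data analysis does not separate technical loss from participant-related loss, which weakens the planned search for patients in whom home EEG is feasible

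*Protocol*

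**What the plan says.** Feasibility of home high-density EEG is the primary objective of Theme 1 (section 2.1.2). For Substudy 1, section 10.2 a) will "Quantify the proportion of missing data for sleep nights with high density EEG". The same item adds a post hoc analysis of "whether any baseline questionnaire outcomes associate with poor data quality (larger levels of missing data"). The parenthesis is the protocol's own definition of the outcome, and it names no cause.

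Section 6.2 gives the purpose of that analysis: to learn "whether any of these questionnaires can help stratify in which patients home EEG will be feasible for future trials".

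Section 9.5 says that "it is possible for data to be lost or not collected due to technological issues (e.g., battery failures"). It gives no rate. After a significant loss, whatever the cause, "participants may be asked if they are willing to repeat an EEG night or blood test if appropriate within the 3 month study period".

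Three provisions touch on reasons for loss:
- Section 14.2.1, under paper CRFs: "All missing data will be explained".
- Section 5.5, on withdrawal: "The reason for withdrawal will be documented in the participant's case report form (CRF) although a reason would not have to be provided".
- Appendix 2: free-text items after the final session on wearing the device and any difficulty with it.

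EEG data arrive by electronic download (sections 8.1.3 and 8.2). No section asks for a cause for each lost EEG night, and none carries a cause into analysis a).

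**The concern.** The outcome fits its purpose poorly. Asking in which patients home EEG is feasible is a question about patients. A questionnaire on sleepiness, mood, apathy or cognition has no evident reason to predict a flat battery. Yet a battery failure and a cap taken off at 2 a.m. count alike in the outcome of the questionnaire analysis.

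Two things are at stake. First, the same missing proportion calls for different action in a later trial depending on its source: equipment faults call for changes to equipment or set-up, while intolerance bears on which patients can be studied this way. Second, technical loss unrelated to the patient adds noise to the outcome and attenuates any real association, so a useful questionnaire is easier to miss.

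**Working it through.** The protocol states no power, effect size or failure rate for this analysis, so there is no figure of its own to reproduce. From the protocol: 3 nights per participant (section 6.3), and 50 participants (section 4.4) or 50–100 (section 10.1). All other inputs are assumptions.

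**1. Direction of the effect.** Let p be the risk of participant-related loss and t the risk of technical loss, with t independent of the questionnaire. The observed risk of poor data is

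q = 1 − (1 − p)(1 − t).

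For two questionnaire groups, q2 − q1 = (1 − t)(p2 − p1). The risk difference shrinks by the factor (1 − t), and the odds ratio moves toward 1.

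Example with p1 = 0.10, p2 = 0.30, one yes/no outcome per participant and two equal groups:
- t = 0: odds ratio (0.30/0.70)/(0.10/0.90) = 3.86.
- t = 0.10: q1 = 1 − 0.90 × 0.90 = 0.19 and q2 = 1 − 0.70 × 0.90 = 0.37. The difference is 0.18 and the odds ratio is (0.37/0.63)/(0.19/0.81) = 2.50.
- Share of poor-data participants who are there through technical loss alone at t = 0.10: 1 − 0.20/0.28 = 29%.

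| t | Observed odds ratio | Power, N = 50 | Power, N = 100 |
|---|---|---|---|
| 0 | 3.86 | 42% | 71% |
| 5% | 2.97 | 35% | 61% |
| 10% | 2.50 | 29% | 52% |
| 20% | 2.02 | 21% | 38% |

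**2. Size with nights as the unit.** In a simulation, the log-odds of participant-caused failure per night are logit(0.10) + ln(2.5)·x + N(0, 0.8²), where x is a standardised questionnaire score. Device failure is independent of x. The test is a Spearman correlation of x with the number of failed nights out of 3, two-sided 5%. The 10% is the rate at the average score; the simulated mean rate is about 15%.

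| Outcome | Mean rank correlation | Power, N = 50 | Power, N = 100 |
|---|---|---|---|
| Participant-caused only | 0.39 | 81% | 98% |
| All causes, device failure 5% | 0.33 | 67% | 94% |
| All causes, device failure 10% | 0.30 | 57% | 87% |
| All causes, device failure 15% | 0.27 | 49% | 79% |

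At device failure of 1% to 2%, pooled power at N = 50 is about 78% and 73–76%. A larger sample restores power but leaves the correlation just as attenuated.

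**3. What imperfect coding does.** The 81% row assumes every participant-caused loss is recognised. Suppose instead that 30% of these losses cannot be attributed, and that none is seen on a night when the device also failed. At N = 50 the cause-specific outcome then has about 65% power against 68% pooled at 5% device failure, and 63% against 59% at 10%. The advantage vanishes at the lower rate and is small at the higher one.

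**The case against.** The strongest case on the other side has five parts.

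- **The all-cause proportion is right for feasibility.** A night lost to a flat battery is lost to a trial, and acceptability is assessed separately in section 10.2 b). This stands. A reader might infer that the feasibility proportion itself is wrong, and the protocol does not support that. But free-text acceptability answers after the final session do not give a cause for each lost night.
- **The causes may be recoverable.** A researcher visits each night and checks data quality (section 6.4.1), and some reasons are recorded. A reader might infer that intolerance can never be told apart from device failure in this study. That goes too far: the planned analysis does not separate them. The existing rules still leave a gap, because section 14.2.1 addresses paper forms and section 5.5 covers withdrawal, not a lost night in someone who continues.
- **Technical loss is only called possible.** This is correct. A reader might take section 9.5 as forecasting device failures, but it gives no rate and describes careful set-up. The 5–15% range is an assumption.
- **The questionnaire analysis is post hoc and exploratory.** This is correct, and no decision rule rests on it. A reader might infer that it will probably come out falsely negative. Pooled power of 67%, 57% and 49% at N = 50 does not support that, and power is higher at N = 100. With an odds ratio of 1.5, power is only about 25% even with perfect coding, so sample size then matters more than pooling.
- **Independence is assumed.** If restlessness loosens electrodes, some apparently technical loss is patient-related, and excluding it would discard signal. This stands, and it is why both outcomes should be reported.

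A statistical analysis plan or CRF could add a cause code. The point does not rest on that omission: the protocol states an outcome for the questionnaire analysis, and that outcome does not match its stated purpose.

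**Conclusion.** The point holds in a limited form. Section 10.2 a) pools all causes of EEG loss in an analysis meant to describe patients, and pooling attenuates real associations if technical loss is unrelated to the questionnaires. The direction follows from the definition; the size depends on rates the protocol does not give. At N = 50, with an odds ratio of 2.5 per SD and device failure of 5% to 15% per night, the loss is about 14 to 32 percentage points of power (81% to 67–49%). At N = 100 it is about 4 to 19 points (98% to 94–79%), and at 1–2% device failure it is only a few points. The overall missing proportion remains valid but should not stand alone. This is a worthwhile, inexpensive improvement to an exploratory analysis and to the reading of the primary feasibility figure; it does not invalidate either.

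**What to change.** - **Record a cause for each lost or partial EEG night:** device or operator; participant (removed, declined, not tolerated); or unclear. Do this at the next nightly visit or at download, while the participant or carer can still be asked.
- **Report the split beside the total.** Keep the all-cause proportion in section 10.2 a) as the feasibility figure.
- **In the post hoc questionnaire analysis, report participant-related and all-cause missing data.** Count unclear losses once as participant-related and once as not.

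The cost is one extra coded field, with no added visits or participants. Some losses will stay unclear, and the cause-specific outcome has fewer events. Its advantage is therefore mainly in interpretation, and a gain in power is not assured.

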#### 2.1.2 Primary Objectives

### Theme 1

2.1.2.1 Feasibility of home high-density EEG (primary objective);

2.1.2.2 Acceptability of home EEG;

#### Theme 2

2.1.2.3 Feasibility of blood biomarkers for AD;

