### 2.2 Hypotheses

### 2.2.1 Primary Hypotheses:

### Theme 1

Home high-density EEG are feasible and acceptable in people with MCI and AD

### Theme 2

• Blood biomarkers are feasible and acceptable in people with MCI and AD.

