- iv) Sleep dependent memory testing a long-term memory word test delivered by the researcher on either the second or third evening of testing (order counterbalanced)
- v) Acceptability participants will be asked to complete a brief questionnaire within 1 week of their final testing session to feedback on their experience (See appendix 2).

### For Substudy 2

Venepuncture of 5-10 ml blood biomarkers taken for analysis of biomarkers (P-tau & NFL, GFAP and abeta42/40, and possibly others in future). In all participants undergoing LP, this will be at the time when bloods are taken alongside LP in any case (i.e. there will be not an extra venepuncture, just more blood drawn). In very rare situations, for example, participants who have another form of biomarker testing (e.g. PET scanning), a new venepuncture will be needed.

As an optional addition, the collected blood sample will also be analysed for *APOE* genotype. The venepuncture already being arranged for blood biomarker analysis will provide a sufficient sample for the additional *APOE* analysis. The *APOE* analysis therefore does not require an additional blood sample/procedure.

As an optional addition, an extra < 5 ml of CSF will be taken during the routine LP for analysis and storage, as long as this does not prolong the procedure by more than 1 minute.

All patients will have had a MoCA cognitive test as part of routine care within 3 months of CSF collection. In the very rare case that this has not happened as part of routine clinical care, we will also carry out a MoCA as close as possible in time to their lumbar puncture (taking into account they might be nervous on the day of the procedure, we may do this at a different hospital visit). As an alternative, we will offer the opportunity to complete the MoCA test remotely via video call and save the need for an additional hospital visit. Several studies have demonstrated that administering the MoCA remotely via video call is a valid and reliable alternative to a face-to-face assessment.

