# Comments

Q26	Do you have any additional comments regarding your sleep?	

Appendix 2

**Sleep AD experience questionnaire** The questionnaire is designed using the Unified Theory of Acceptance and Use of Technology (UTAUT) model to determine the factors that determine user acceptance of technology these include performance expectancy, effort expectancy, social influence, attitude, and facilitating conditions.

Question	Response format
How did you feel about taking part in the SleepAD study?	Free text
Did your experience of wearing the EEG match your expectations (or was it better or worse)?	Free text
What did you think about wearing the EEG device before testing?	Free text
Did you encounter any difficulty or notice benefits from using the EEG device?	Free text
Do you think it's a good/interesting idea to use an EEG device to measure your sleep and do blood testing?	Free text
Did anyone encourage you to continue the study?	Free text
What did your family/friends think about you getting involved in this study?	Free text
How did you find the process of blood testing?	Free text
Would anything make the process easier for you in the future?	Free text

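### Section 10.2 plans to calculate acceptability ratings for home EEG, but every item of the only acceptability questionnaire is free text, and no analysis of blood-test acceptability is listed although a primary hypothesis claims it.

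*Protocol*

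**What the plan says.** Section 2.1.2 places "2.1.2.2 Acceptability of home EEG" under Primary Objectives for Theme 1. The Theme 1 primary hypothesis in 2.2.1 reads "Home high-density EEG are feasible and acceptable in people with MCI and AD". The matching analysis, 10.2 Substudy 1 item b), is to "Calculate acceptability ratings for home EEG". It gives no scale, score or summary.

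The data source is 6.3 item v), under Substudy 1: "participants will be asked to complete a brief questionnaire within 1 week of their final testing session to feedback on their experience", with a pointer to Appendix 2. That appendix prints a response format beside each question, and the format is free text throughout. A typical item is "Did you encounter any difficulty or notice benefits from using the EEG device".

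For Theme 2, the primary hypothesis in 2.2.1 is "Blood biomarkers are feasible and acceptable in people with MCI and AD", while the primary objective in 2.1.2 is only "2.1.2.3 Feasibility of blood biomarkers for AD". The Substudy 2 analyses in 10.2 deal with sample loss, data completeness, diagnostic accuracy, sleep associations, assay validation and conversion to AD. None concerns acceptability.

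**The concern.** A rating is something a participant gives on a scale. If the form offers no scale, an analysis plan can summarise only what somebody else later reads into the answers. That would be an assessor's classification, a different quantity from the one promised in 10.2.

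Section 1.1 says the programme will supply acceptability data to feed directly into clinical trials. A trial team planning home EEG will want to know what proportion of people with MCI or early AD found it acceptable, and how precisely that is known. Free text alone does not give this. It cannot be recovered reliably later either, since the form is due within a week of testing and respondents have memory impairment.

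The blood-test claim has a related gap. It is stated as part of a primary hypothesis, but no listed analysis would support or contradict it.

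**Working it through.** The protocol gives no figure to reproduce here, so the check is a comparison of sections and a count of items.

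**Step 1: what the questionnaire yields.** Appendix 2 has nine questions.

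| Property | Count |
|---|---|
| Items in total | 9 |
| Items with free-text response | 9 |
| Items with a scale, score or fixed answer options | 9 − 9 = 0 |
| Items that mention blood testing | 2 |
| Of these, items on blood testing alone | 1 |

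The second blood item asks about the EEG device and blood testing in one question, so an answer cannot always be assigned to either. The EEG item quoted above also asks two things at once (difficulty and benefit). Both features make later coding harder.

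**Step 2: objective, data and analysis side by side.**

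| Claim | Status | Data collected | Analysis in 10.2 |
|---|---|---|---|
| Home EEG is acceptable | Under Primary Objectives (2.1.2) and in the Theme 1 primary hypothesis | Free text, Sub-study 1 | Ratings, item b) |
| Blood biomarkers are acceptable | In the Theme 2 primary hypothesis only | Two free-text items, Sub-study 1 | None in either sub-study |

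In the first row the analysis does not fit the data. In the second row there is no analysis.

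**Step 3: who receives the form.** Sections 6.3 and 8.2 mention the questionnaire for Sub-study 1 only. For Sub-study 2, section 8.2 lists extraction from medical records and a single venepuncture. Section 6.3 adds optional samples and, if needed, a MoCA. A person in Sub-study 2 alone is therefore never asked. The protocol does not say how many such people there will be.

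**Step 4: people who stop early.** Section 6.3 ties the form to the participant's last testing session. Section 8.2 places it after three nights of EEG. Section 11.4.1 says a participant who withdraws will be replaced. No section says whether someone who stops after one or two nights is given the form, so this is left open.

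**The case against.** The best defence is that free text can be analysed. Appendix 2 names a framework (UTAUT) and its domains, one item invites an ordered answer (better or worse than expected), and a coding scheme could sit in a statistical analysis plan that is not at hand. This stands to the extent that the questionnaire is not worthless and a qualitative analysis is possible. It does not rescue the word *ratings*, because a later plan can define coding but cannot create scores that participants never gave.

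A second defence is that Theme 2 and Sub-study 2 are different things. The hypothesis concerns people with MCI and AD. Sub-study 1 enrols that population, takes blood from them and asks about it. This is correct, so some relevant text will exist. There is still no rating and no listed analysis of it.

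Three stronger readings may tempt a reader, and the protocol supports none of them:

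- **That no Sub-study 2 participant is surveyed.** Section 3 allows the two groups to overlap, and section 4.1 expects many lumbar-puncture patients to join the EEG part, where they would receive the form. Only people in Sub-study 2 alone are missed.
- **That early stoppers are excluded.** For someone who stops after one night, that night can be read as the final session. The wording is ambiguous and does not state an exclusion. No size for any resulting bias can be derived from the protocol.
- **That acceptability is co-primary.** The protocol does not use that term. Acceptability sits under the Primary Objectives heading, but only EEG feasibility is tagged as the primary objective.

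**Conclusion.** The point holds in two parts. First, the EEG acceptability analysis cannot be carried out as worded: 0 of 9 items give a participant rating, and the protocol itself fixes both the analysis and the response format. Second, acceptability of blood testing is claimed in a primary hypothesis with no listed analysis. Its data are limited to two free-text items in Sub-study 1, and nothing is collected from people in Sub-study 2 alone.

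It would go too far to say that acceptability cannot be studied at all, since qualitative analysis remains possible. The conclusion assumes only that Appendix 2 is the complete instrument, and no other acceptability measure is described. Early stoppers are a point to clarify, and replacement of withdrawn participants makes it worth doing. The effect is confined to the acceptability claims; EEG feasibility, measured by missing data, does not depend on it.

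**What to change.** 1. **Appendix 2.** Add a small number of scored items for home EEG and, separately, for blood testing, for example 5-point items plus willingness to repeat. Keep the free text to explain the scores.
2. **Section 10.2.** State what response counts as acceptable, and report the proportion for EEG with a 95% confidence interval. Add the same analysis for blood testing.
3. **Section 6.3 v).** State that the form goes to everyone with at least one attempted EEG night, including those who stop early and agree to complete it. Align 8.2 with this.
4. **Theme 2.** Either give the scored blood-test item to Sub-study 2 participants, or limit the acceptability part of the Theme 2 hypothesis to Sub-study 1.

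The cost is a minor amendment and about one extra minute per participant. The drawback is that people already surveyed will lack scores, so the proportions would rest on later participants. If that is not acceptable, the minimum change is to reword 10.2 b) as a prespecified qualitative analysis and drop the reference to ratings. This keeps all responses comparable but gives no participant-rated proportion. Items 3 and 4, and a listed analysis of the blood-test answers, would still be needed.
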